#### Visit to Confirm a Suspected Virologic Failure

Confirmed virologic failure is defined as two consecutive HIV-1 RNA levels ≥200 copies/mL by real-time HIV-1 RNA testing. Participants with a plasma HIV-1 RNA ≥200 copies/mL at any visit will have a confirmatory viral load obtained as soon as possible but within 14 days after the first sample was drawn, if possible. If this visit coincides with a regularly scheduled visit, the evaluations should be combined. If the consecutive measurement of HIV-1 RNA is also ≥200

copies/mL, the participant will be considered to have confirmed virologic failure and the protocol core team must be notified via e-mail [contact] within 48 hours.

If a participant is confirmed to have virologic failure, then the participant must discontinue study treatment and return to the clinic within 14 days after discontinuing study treatment to complete the premature treatment/study discontinuation evaluations. The participant will then continue to be followed on study/off study treatment as per section 6.1.

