#### 6.3.1.2 Diagnoses

Post-entry, record any of the following diagnoses that are newly diagnosed or participant reported since the last visit on the AE log:

CDC category B/C diseases, diabetes mellitus, hypertension, myocardial infarction (MI), coronary artery disease (CAD) (not MI), congestive heart failure (not HIV cardiomyopathy), stroke, malignancy (excluding basal cell cancer of the skin), renal insufficiency, liver disease, bleeding or coagulation disorders, and any inflammatory condition including, but not limited to, systemic illness or genital infections requiring antimicrobial therapy, immune reconstitution inflammatory syndromes, lupus, rheumatoid arthritis, or inflammatory bowel disease.

NOTE: Cutaneous non-inflammatory conditions not requiring antimicrobial therapy do not need to be reported as an AE on the AE log.

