#### 6.3.15 Immunologic Studies

Because of the diurnal variation in biomarkers that may be measured as part of the study (eg, CD4+ and CD8+ T-cell counts and other biomarkers that may be measured on stored samples), blood draws for individual participants should be performed consistently in either the morning or the afternoon throughout the study, if possible.

NOTE: If a participant experiences an inflammatory condition (ie, infection requiring hospitalization, a systemic viral illness such as an influenza-like illness, a severe drug hypersensitivity reaction, or a fever on the day of visit defined as T° >38°C), receives a vaccine or experiences a concurrent illness, wait 7 days for blood draw.

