# 9.6 Analyses

All statistical tests will be two-sided with a nominal alpha level of 0.05. Because this is a phase II study and all potential biologic activities of the intervention are of interest, analyses will be as-treated, and limited to participants who 1) have baseline and week 26 sCD14 measurements, 2) remain on study product through week 26 (participants with more than 50% on average of missed study product may be excluded), 3) have not used prohibited medications, 4) do not have a confirmed virologic failure (as defined per section 6.2.3 at or prior to week 26, and 5) do not experience inflammatory conditions, receive vaccines, or have concurrent illness (as defined per section 6.2.3).

NOTE: Participants experiencing inflammatory conditions at the time of a visit are instructed to wait 7 days before measurements are obtained. Measurements obtained while inflammatory conditions are present will not be included in the analysis. A supplemental intent-to-treat analysis will also be performed and will include all randomized participants. No adjustment for multiple testing will be performed. A summary of the number of participants experiencing study product-related AEs and the types of AEs will be reported, as will the proportion of participants who discontinue study product after entry.

To reduce intra-participant variability, two blood draws will be performed at baseline (entry and week 2) and week 26 (week 25 and week 26) and the measurements will be the average of two for sCD14. If repeat measurements are not available at either of these time points, a single measurement will be used rather than the average.

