4.1 Analysis Populations

Intent-To-Treat (ITT): All randomized participants.

Modified Intent-To-Treat (mITT): All randomized participants who started study product.

Per-Protocol (PP): All eligible, randomized participants who 1) have baseline and week 25/26 sCD14 measurements, 2) remain on study product through week 26 (participants with more than 50% on average of missed study product may be excluded), 3) have not used prohibited medications, 4) do not have a confirmed virologic failure (as defined per section 6.2.3 at or prior to week 26, and 5) do not experience inflammatory conditions, receive vaccines, or have concurrent illness (as defined per section 6.2.3).

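### Per-protocol criterion 5 removes whole participants, with no time limit, for events that the plan's other rules handle draw by draw, and its cross-references define none of its terms

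*SAP*

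**What the plan says.** Protocol 9.6 makes the as-treated set primary: "analyses will be as-treated, and limited to participants who 1) have baseline and week 26 sCD14 measurements", followed by four further criteria. SAP 4.1 repeats these as the PP population, and SAP 4.4 uses PP for all continuous outcomes. Criterion 5 in both documents admits only participants who "do not experience inflammatory conditions, receive vaccines, or have concurrent illness (as defined per section 6.2.3". A5352s 9.6 has the same criterion but refers to A5350 section 6.3.7.

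Other rules cover the same events:

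- **Protocol 6.3.15** lists inflammatory conditions: infection needing hospitalisation, systemic viral illness, "a severe drug hypersensitivity reaction, or a fever on the day of visit defined as" a temperature above 38°C. For these, or if the participant "receives a vaccine or experiences a concurrent illness, wait 7 days for blood draw".
- **Protocol 9.6 NOTE**, directly after the criteria: "Participants experiencing inflammatory conditions at the time of a visit are instructed to wait 7 days before measurements are obtained". It adds: "Measurements obtained while inflammatory conditions are present will not be included in the analysis". A5352s 9.6 has an equivalent NOTE.
- **SAP 4.4** does not use specimens taken within 6 days of an influenza vaccination, except where both fall on one date and the site documents that the vaccine came second.
- **SAP 4.3 and Protocol 9.6** allow a single value where the second of a pair is missing.

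**The concern.** Criterion 5 decides who is in the primary analysis, and as written it does not match the rules that decide which specimens are usable. The plan tells sites to wait 7 days and then draw, but a literal reading excludes the participant who did so. Vaccines are not on the Protocol 5.4.2 prohibited list, so a participant can be vaccinated within the protocol and still leave the primary set.

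sCD14 is an inflammation marker. Excluding everyone with an inflammatory illness after randomisation selects on something close to the outcome, and possibly related to treatment, more than specimen validity requires. One programmer could drop the person and another only the specimen, both citing this SAP.

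**Working it through.** **1. Cross-references.** Protocol 6.2.3 covers visit timing, fasting and virologic failure: "Confirmed virologic failure is defined as two consecutive HIV-1 RNA levels" at or above 200 copies/mL. That defines criterion 4's term and none of criterion 5's. Clarification Memo 1 adds only fasting to 6.2.3. Section 6.3.7, cited by the substudy, is Weight. The three copies of the criterion thus carry two different wrong references. Section 6.3.15 is the only other place that names inflammatory condition, vaccine and concurrent illness together. It does not define concurrent illness or say when its 7 days start.

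**2. Time limits.** Criteria 2 and 4 stop at week 26. Criterion 3 has no stated limit, but Protocol 5.4.2 confines the prohibition to time on study agents. Criterion 5 has no limit, and follow-up runs to week 38.

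**3. Both readings applied to four hypothetical participants.** The primary draws are at entry, week 2, week 25 and week 26.

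| Participant | Draw and specimen rules | Criterion 5 as written |
|---|---|---|
| Influenza vaccine at week 10 | Nearest primary draws are 8 weeks before and 15 weeks after; all four values valid | Excluded |
| Fever on the day of the week 25 visit, draw postponed 7 days | Value valid and inside the SAP window of weeks 23 to 28 | Excluded |
| 6.3.15 illness at week 32 only | All four primary draws already taken | Excluded |
| Influenza vaccine 3 days before the week 25 draw, week 26 draw 7 days later (day 10) | Week 25 value dropped, week 26 value used alone | Excluded |

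**4. Effect on SAP 4.4.** Every participant whom the influenza rule could touch has received a vaccine, so literal criterion 5 has already removed them from PP. Protocol 4.2.5 bars vaccination in the 2 weeks before entry, and PP requires eligibility, so pre-entry vaccination leaves no gap. The rule and its same-day exception could act only in the supplemental ITT analysis.

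**5. Width of the two rules for a vaccination.** Counting days 0 to 6 after vaccination, the four primary draws are exposed on at most 4 × 7 = 28 days. The literal criterion covers 38 × 7 = 266 days, and 28/266 = 10.5%. The 28 is an upper bound, because the week 25 and 26 windows can overlap and the entry window falls mostly before the study. This compares calendar time and does not count participants.

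**6. Sample size.** The planned figure reproduces. With a difference of 0.07, SD 0.09, two-sided alpha 0.05 and 90% power, the t-based solution is 35.73, so 36 per arm; 36/0.80 = 45 per arm, 90 in total. With 36 per arm, power is 90.2%. This figure is not disputed.

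**7. Why no power claim follows.** The documents give no event rate, so any extra exclusion is an assumption. Noncentral-t power from 36 per arm, with n rounded to the nearest integer:

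| Assumed extra exclusion | n per arm | SD 0.09 (planning) | SD 0.06 (averaged pairs) |
|---|---|---|---|
| 0% | 36 | 90.2% | 99.8% |
| 10% | 32 | 86.5% | 99.6% |
| 20% | 29 | 82.9% | 99.2% |
| 30% | 25 | 76.9% | 98.1% |

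Keeping participants can also cost precision. Suppose 20% stay in with single values at both time points (SD 0.11), while the rest have pairs (SD 0.06). The variance is 0.8 × 0.06² + 0.2 × 0.11² = 0.0053, the SD 0.073, and power at 36 per arm 98.0%. That is below the 99.2% from excluding them.

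**The case against.** The strongest reply is that this is a cross-reference slip with obvious intent. Section 6.3.15 has all three terms in the same order, the NOTE follows criterion 5 directly and drops measurements, and the same-day exception in SAP 4.4 would be pointless in PP if any vaccine removed the participant. Much of this stands: the target is clear and specimen-level intent is recoverable. But the NOTE does not override the criterion beside it, covers inflammatory conditions only, and is not in the SAP. SAP 4.4 covers influenza vaccine only. Other vaccines and illness have no specimen rule in the SAP.

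A second reply is that the ITT analysis is a backstop. Protocol 9.6 does plan one, as supplemental; SAP 4.1 defines the population, but SAP 4.4 assigns no analysis to it.

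A reader might infer three stronger points that the documents do not support:

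- **That inflammatory condition has two equally plausible definitions**, because Protocol 6.3.1.2 speaks of "any inflammatory condition including, but not limited to, systemic illness or genital infections requiring antimicrobial therapy". That is an adverse-event reporting list and names neither vaccines nor concurrent illness.
- **That the trial is underpowered, or that the fix raises power.** Without an event rate neither can be shown, and steps 6 and 7 show that the direction depends on the SD and on how many pairs stay complete.
- **That a specimen rule removes the selection.** It reduces it. Criteria 2 to 4 also select after randomisation, by design.

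**Conclusion.** The concern holds as a defect in the wording of the primary analysis set. It is certain from the text that criterion 5 is a participant-level exclusion without a time limit, that its references define none of its terms, and that the matching rules act on draws, measurements or specimens. Followed as written, it removes participants with fully valid primary specimens and leaves the SAP influenza rule nothing to act on in PP analyses. How many participants this would affect is unknown, and the conclusion does not depend on any assumed rate. It should be fixed before unblinding, because it determines who is in the primary set.

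**What to change.** 1. **SAP 4.1 and Protocol 9.6.** Replace criterion 5 with a specimen-level rule that refers to A5350 6.3.15. A specimen is not used if it was collected while a 6.3.15 condition was present, or inside the 7-day wait after such a condition or a vaccine. A participant stays in PP if at least one valid baseline and one valid on-treatment week 25/26 sCD14 value remain and criteria 1 to 4 are met. The team must state when the 7 days start and what concurrent illness covers, since the documents settle neither. Criterion 4 keeps its reference to 6.2.3.
2. **SAP 4.4.** Carry the Protocol 9.6 NOTE into the SAP. Extend the influenza sentence, with its same-day exception, to all vaccines as in 6.3.15.
3. **A5352s 9.6.** Replace the reference to 6.3.7 with A5350 6.3.15 and make criterion 5 measurement-level, in line with the NOTE already there. Because 6.3.15 speaks only of blood draws, state whether vaccines and concurrent illness are handled the same way for biopsies and lactulose/mannitol tests.
4. **Reporting.** Give, by arm, the specimens dropped and the participants left with a single value.

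The cost is a wording change with no new visits. Some participants will contribute one value in place of an averaged pair, which the plan already allows but which is less precise (protocol SDs 0.11 single, 0.06 averaged). The rule also needs dates: SAP 4.4 implies that influenza vaccination dates are held, but the Protocol 6.3.4 list used for post-entry medication recording does not name vaccines. The source of vaccine and illness dates must be confirmed before database lock.

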4.2 Participant Exclusion

Participants found to be ineligible for A5350 by the site, study statistician(s), or data manager will be reviewed by the study co-chairs for confirmation of their ineligibility.

4.3 Analysis Visit Windows

For all analyses, the following visit windows will be used:

- Screening: evaluations completed within 45 days of randomization.
- Entry (week 0): entry evaluations must occur on/after randomization and at least 24 hours after screening.
- Week 2: pre-treatment evaluation scheduled within a week [1, 3] window but prior to treatment initiation, treatment must begin within the next 72 hours after evaluation.
- On-treatment evaluations:
 - Week 4: weeks (3, 5]
 - Week 6: weeks (5, 8]
 - Week 14: weeks [12, 16]
 - Week 25 & 26: weeks [23, 28]
- Week 38: post-treatment evaluation scheduled within a week [36, 40] window.

If multiple results are available within the Week 6 or 14 visit windows the result closest to the scheduled visit will be used. If multiple results are available within the Week 38 window the result closest to 12 weeks after the last dose of study treatment (corresponding to protocol-defined 12 week washout) will be used.

Results within the weeks [23, 28] visit window will use the following logic to determine Week 25 and Week 26 results:

- If two results are collected on treatment the earlier will be Week 25 and the latter Week 26.
- If two results are collected off treatment the earlier will be Week 25 and the latter Week 26.
- If one result is collected on treatment and one result is collected off treatment the on treatment will be Week 25 and the off treatment Week 26.
- If only one result is collected it will be Week 25.
- If three or more results are available priority will be given to those collected on treatment and assigned Weeks based on the above rules.

For markers run in duplicate at entry and Week 2 and also at Weeks 25 and 26, "baseline" will refer to the average of entry and Week 2 and "Week 25/26" will refer to the average of Week 25 and Week 26. If only one result is available at either of these time points the single result will be used. For per-protocol analyses the "Week 25/26" calculation will only use results collected while on treatment.

4.4 Statistical Summaries and Testing

All statistical tests will be two-sided with a nominal alpha level of 0.05 and no adjustment for multiple testing.

Specimens collected 1 day after the last dose of study treatment will be considered "on treatment".

Specimens collected within 6 days of an influenza vaccination will not be used for analysis unless the vaccination and specimen collection occurred on the same date and the site has documented that the vaccination was given after specimen collection.

Outcome measures will be transformed for analyses and summaries on the log₁₀ scale, as appropriate, if determined to not be approximately normally distributed.

Because the stratification is to ensure balance between the treatment arms within A5352s and is not felt to affect A5350 outcomes, the stratification will not be taken into account in analyses.

Safety analyses will summarize the highest grade AE by participant using the mITT population and will compare treatment arms using the Wilcoxon rank-sum test. All AEs and AEs related to study treatment will be analyzed.

For all continuous outcome measures, tabular and graphical data summaries will be provided for both cross-sectional values across study weeks and change from baseline to post-baseline study weeks and will use the PP population. Mean changes in outcome measures will be compared between arms with either a two-sample t-test with equal variances or an adjusted linear regression model, as appropriate. The mean difference and 95% confidence interval (CI) will be provided along with the associated p-value.

For the primary analysis, two supplemental linear regression analyses will be performed. The first will additionally adjust for baseline sCD14 values (continuous) while the second will assess differential Visbiome Extra Strength

effects by baseline sCD14 tertile by additionally adjusting for the sCD14 tertile main effect and the study arm by sCD14 tertile interaction.

Correlations will be assessed with scatter plots as well as the Spearman correlation coefficient and associated p-value using the PP population.

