#### 9.3 Randomization and Stratification

After eligibility is confirmed, participants will be randomized at a 1:1 ratio (Visbiome Extra Strength: placebo) using permuted blocks without institutional balancing with stratification by intent and eligibility to enroll in the substudy A5352s. Because the stratification is to ensure balance between the treatment arms within A5352s and is not felt to affect A5350 outcomes, the stratification will not be taken into account in analyses.

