# 9.4 Sample Size and Accrual

The primary objective of this study is to compare sCD14 change over 24 weeks of treatment in participants randomized to Visbiome Extra Strength compared to placebo. The sample size calculations are based on the primary hypothesis testing  $H_0$ :  $\mu_{Visbiome\ Extra}$  strength =  $\mu_{placebo}$  targeting 90% power in the comparison of changes in  $log_{10}$ -transformed sCD14 between Visbiome Extra Strength and placebo.

Our estimate of the standard deviation for the change in plasma sCD14 levels over 24 weeks of treatment comes from a recent placebo-controlled trial of maraviroc intensification among ART-suppressed, HIV-infected individuals [98]. Among the 20 placebo-treated participants, the mean change in plasma sCD14 levels from baseline to week 16 was +0.003 log10 ug/ml (SD: 0.11) when analyzing a single measurement at each time point and -0.005 log10 ug/ml (SD: 0.06) when taking the average of two measures at each time point. Although we plan to take the average of two sCD14 levels at both baseline and week 26, we have conservatively powered the study assuming the SD is 0.09 log10 ug/ml.

A 0.07 log10 sCD14 between-arm difference was associated with a 23% decreased odds of a non-AIDS event or non-accidental death at the pre-event time point [56] and is considered as clinically significant, and therefore was chosen as the effect size for this study.

A total sample of 90 participants (45 per arm) is needed to detect a difference of 0.07  $log_{10}$  in sCD14 levels between Visbiome Extra Strength and placebo with 90% power and a 0.05 two-sided type I error rate, under the assumption that the SD of the changes in  $log_{10}$  sCD14 from baseline to week 26 is 0.09 for both arms.

Although it is expected that Visbiome Extra Strength will be well tolerated in this study, it is anticipated that there will be some missing data due to laboratory complications and loss to follow-up. The sample size is inflated by 20% to account for missing data.

The following table summarizes the calculation of the sample sizes corresponding to the detection of various effect sizes under various assumed standard deviations, with the effect size, standard deviation, and adjusted sample size selected for this study shown in bold.

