Effect size in log 10 sCD14 (difference between Visbiome Extra Strength and placebo)	Std Dev of ∆ Baseline to Week 26	Total Sample size (90% power, alpha=0.05)	Adjusted Sample Size (20% inflation)
0.03	0.05	60*2=120	75*2=150
	0.07	116*2=232	145*2=290
	0.09	191*2=382	239*2=478
0.05	0.05	23*2=46	29*2=58
	0.07	43*2=86	54*2=108
	0.09	70*2=140	88*2=176
0.07	0.05	12*2=24	15*2=30
	0.07	23*2=46	29*2=58
	0.09	36*2=72	45*2=90

For each continuous secondary endpoint, change from baseline to week 26 will be compared between treatment arms. The following table summarizes the power to detect various effect sizes as well as the precision of the effect size estimate.

Comparison of 2 arms (36 vs. 36 evaluable participants)				
Effect Power Width of 95% Size CI				
0.77*SD	90%	± 0.47*SD		
0.67*SD	80%	± 0.47*SD		
0.59*SD	70%	± 0.47*SD		

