#### 9.6.1 Primary Analysis

The primary objective of the study is to assess the effect of Visbiome Extra Strength on sCD14 in HIV-infected participants well-controlled on ART. To address this, changes in sCD14 from baseline to week 26 will be compared between the Visbiome Extra Strength arm and the placebo arm by linear regression. For this model each participant will have a single outcome measure of sCD14 change from baseline to week 26. The only predictor variable will be study arm.

Two supplemental linear regression analyses will be performed. The first will additionally adjust for baseline sCD14 values (continuous) while the second will assess differential Visbiome Extra Strength effects by baseline sCD14 tertile by additionally adjusting for the sCD14 tertile main effect and the study arm by sCD14 tertile interaction.

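### Randomisation is stratified by A5352s intent and eligibility, but the linear models for continuous A5350 outcomes omit the stratum and so give up precision that costs almost nothing to keep

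*SAP*

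**What the plan says.** Protocol 9.3 specifies 1:1 allocation in permuted blocks with "stratification by intent and eligibility to enroll in the substudy A5352s". The same section, and SAP 4.4, then exclude that factor from the models. Both instruct that "the stratification will not be taken into account in analyses". The reason that both offer for this is as follows: "Because the stratification is to ensure balance between the treatment arms within A5352s and is not felt to affect A5350 outcomes".

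The models follow from this. For the primary comparison, Protocol 9.6.1 states "The only predictor variable will be study arm", and 9.6.2 repeats the rule for the secondary outcomes. Protocol 9.6.1 continues "Two supplemental linear regression analyses will be performed"; these add baseline sCD14, or its tertile with an arm interaction, but not the stratum. For continuous outcomes SAP 4.4 allows "either a two-sample t-test with equal variances or an adjusted linear regression model, as appropriate". It names no covariates for that option, and the same section rules the stratification out. No sensitivity analysis with the stratum is planned.

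**The concern.** Two reasons are given for leaving the stratum out. The first, that it serves balance within A5352s, explains why the factor was used but has no bearing on the standard error of the A5350 comparison. The second, that it is not thought to affect A5350 outcomes, comes without data. Nothing in the documents contradicts it either.

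Stratified randomisation removes most of the between-stratum variation from the error of the arm difference. A model without the stratum still counts that variation as residual noise. If the stratum predicts the outcome, the reported standard error is then larger than the true one. The outcome is change from baseline, so only a stratum difference in change matters; a stable difference in level cancels.

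Such a difference is plausible but not shown. The substudy has stricter entry criteria (A5352s 4.1 and 4.2), including exclusion of irritable bowel syndrome. Its participants have colonic biopsies at entry and at week 24, close to the sCD14 draws at entry, week 2, week 25 and week 26.

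At stake is the width of the intervals for the primary and continuous secondary outcomes. The Wilcoxon safety tests, the Spearman correlations and the A5352s analyses are not affected.

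**Working it through.** **Inputs.** Protocol 9.4 gives a target difference of 0.07 log10, 90% power, two-sided alpha 0.05, and an SD of change in "sCD14 from baseline to week 26 is 0.09 for both arms". The secondary-endpoint table gives "Comparison of 2 arms (36 vs. 36 evaluable participants"). The substudy plans 40 of the 90 participants, with 16 evaluable per arm (A5352s 9.4), so the main split within each arm is 16 substudy and 20 other. The one-in-three rule in Protocol 3.0 suggests 12/24 as an alternative. The stratum difference in change, *d*, is an assumption, shown as a range.

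**The plan's own figure.** A two-sample t-test (noncentral t) with difference 0.07 and SD 0.09 needs 36 per arm, with power 90.2%. Then 36/(1 − 0.20) = 45 per arm, 90 in total. This reproduces the protocol. The arm-only SE is 0.09 × √(2/36) = 0.0212. The half-width of the 95% CI is 1.9944 × √(2/36) = 0.47 SD, also as stated.

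**Formula.** With a stratum share *p* and a total SD fixed at 0.09, the stratum explains R² = p(1 − p)(d/0.09)². The arm-only interval is too wide by a factor of about 1/√(1 − R²). For p = 16/36, p(1 − p) = 0.2469:

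- d = 0.25 SD: R² = 0.015, factor 1.008
- d = 0.5 SD: R² = 0.062, factor 1.032
- d = 1 SD: R² = 0.247, factor 1.152

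**Simulation.** 200,000 trials per cell, arms exactly balanced within strata, total SD held at 0.09. Ratios come from unrounded half-widths.

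| Stratum gap *d* (log10) | Half-CI, arm only / with stratum | Ratio | Type I error, arm only / with stratum | Power, arm only / with stratum |
|---|---|---|---|---|
| 0 | – | – | 5.0% / 5.0% | 90.3% / 90.3% |
| 0.0225 (0.25 SD) | 0.0422 / 0.0418 | 1.008 | 4.8% / 5.0% | 90.4% / 90.7% |
| 0.045 (0.5 SD) | 0.0422 / 0.0409 | 1.033 | 4.3% / 5.0% | 90.8% / 91.9% |
| 0.09 (1 SD) | 0.0423 / 0.0366 | 1.157 | 2.4% / 5.0% | 93.0% / 96.3% |

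The last row is an upper case, because that gap exceeds the 0.07 target effect.

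**Variations.**

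- Split 12/24: the arm-only interval is 0.7%, 3.0% and 13.7% too wide.
- 45 per arm randomised 20/25, with 9 per arm lost at random so that strata are no longer exactly balanced (40,000 trials): arm-only type I error is 5.0%, 4.6% and 2.9%. The interval is 0.6%, 3.2% and 15.4% wider than the adjusted one. The simulation error of a 5% rate is √(0.05 × 0.95/40,000) = 0.1 percentage point, so the first of these cannot be told apart from 5%.
- Total SD 0.06, the value reported in Protocol 9.4 for averaged duplicates: power is at least 99.8% with either model.

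**Cross-check by R².** A separate simulation (40,000 trials, 36 per arm, stratum share 44%) gave the same mean estimate under both models: 0.000 under the null and 0.070 under the alternative, to within 0.0002. At R² = 0.05, 0.10 and 0.20 the arm-only type I error was 4.6%, 3.9% and 2.9%, against 5.1% at each with the stratum. Power was 90.7% against 91.5%, 91.3% against 93.0%, and 92.4% against 95.3%.

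**The case against.** The strongest reply is that this is a deliberate choice, stated identically in both documents. It does not invalidate the estimate or inflate type I error, and 90% power is met either way. Nothing in the documents shows that the stratum predicts change. In the placebo data cited in Protocol 9.4 the mean change was near zero and the two-measure SD was 0.06, so a gap of 0.09 would be 0.09/0.06 = 1.5 of those SDs. At a gap of 0.5 SD the half-width shrinks by only 0.0422 − 0.0409 = 0.0013 log10, about 2% of the target effect. All of this stands, and it makes the expected gain small.

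Three further points limit the gain:

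- The substudy may be cut if enrolment is slow (A5352s 9.4). With a 10% share and a gap of 0.5 SD, R² = 0.09 × 0.25 = 0.0225 and the excess width is 1.1%.
- Continuous outcomes are summarised in the per-protocol set, where exclusions after randomisation can disturb balance. The claim of no bias is exact only for the randomised set, and a stratum term does not cure selection through those exclusions.
- CD4+ change by arm was planned for closed monitoring reports that go to the study statisticians (SAP 2.11.2). The argument that the change precedes any result therefore holds for sCD14 and the other batch-assayed markers, but not for CD4+ outcomes.

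The plan also already seeks precision through averaged duplicate draws and a baseline-adjusted supplemental model. None of this makes the stratum term harmful or supplies data for leaving it out.

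**Conclusion.** The concern holds as a conditional point about precision. Both documents omit a factor that the randomisation balances, and if it predicts change the arm-only interval is too wide and the test conservative. The excess width is under 1% at a gap of 0.25 SD, about 3% at 0.5 SD, and about 14% to 16% in the upper case of 1 SD. These figures assume 36 evaluable per arm, a total SD of 0.09, a substudy share of 33% to 44%, and exact balance or loss at random; block size is not stated. The gap itself is assumed throughout. The sample size needs no change. Because inclusion costs almost nothing if the stratum turns out to be irrelevant, the change should be made, but the planned analysis is not invalid without it.

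**What to change.** Before unblinding, replace the exclusion sentence in SAP 4.4 and Protocol 9.3, and the arm-only rule in Protocol 9.6.1 and 9.6.2, with wording such as:

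> The linear models for the primary and continuous secondary outcomes, including both supplemental sCD14 models, contain study arm and the randomisation stratum (A5352s intent and eligibility as randomised, yes/no). The arm-only two-sample t-test is reported as a sensitivity analysis. The Wilcoxon safety tests, the Spearman correlations and the A5352s analyses are unchanged.

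This also settles which covariates the SAP's adjusted-model option contains for these comparisons.

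Statistically the cost is one degree of freedom. The critical t rises from 1.9944 to 1.9949 (70 to 69 df) in the main model, an increase of 0.025%. It rises by 0.026% in the baseline-adjusted model (69 to 68 df) and by 0.029% in the tertile model (66 to 65 df). With no stratum effect, power is 90.3% either way.

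Administratively, SAP section 1 allows modification. The protocol edits would go through the approval and registration steps that Protocol 4.3.1 sets for an amendment. Stored specimens are assayed only after follow-up ends, so the change can precede any sCD14 result. For CD4+ count and CD4+/CD8+ ratio, the SAP should record when the change was made relative to the closed reports.
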